3.2 Scientific Rationale for Study Design

Botulinum Toxin-A (BTA) inhibits the release of acetylcholine at the neuromuscular junction, thus preventing further muscle contraction, resulting in paralysis of the affected muscles (3). It is reasonable to expect that those with pain associated with the muscles of mastication will have relief with BTA injection. The clinical significance would be substantial if BTA injections are found to reduce myofascial pain as this has classically been difficult to treat. Prior investigations have been conducted to demonstrate the clinical effectiveness of Botulinum Toxin-A (BTA) for reduction in pain associated with myofascial pain disorder (4). However, no double-blinded randomized controlled clinical trials have been conducted. The existing evidence is suggestive of a reduction in pain from BTA injections, however there has not been a robust demonstration of this in the literature.

3.3 Justification for Dose

Not Applicable

3.4 End of Study Definition

A participant is considered to have completed the study if he or she has completed the initial treatment visit and all three of the follow-up visits required for the study. The end of the study is defined as completion of the last visit or procedure shown in the SoA in the trial globally.

4. Subject Selection

4.1 Study Population

Eligible participants in the clinical trial will be male and female adults ages 18-65 identified as having a myofascial pain diagnosis according to the research diagnostic criteria. All subjects will have myofascial pain disorder. Healthy controls will not be involved in the study.

4.2 Inclusion Criteria

- 1. 18 65 years of age
- 2. Able to give informed consent
- 3. Myofascial pain of masticatory muscles as defined according to the RDC/TMD criteria
- 4. Baseline pain measured by the subject ≥ 3.5/10 on visual analog scale

4.3 Exclusion Criteria

- 1. Baseline pain measured by the subject < 3.5/10 on visual analog scale
- 2. Central/neuropathic pain disorder affecting the masticatory muscles
- 3. Temporomandibular joint arthralgia that is more severe than the myofascial pain disorder affecting the masticatory muscles
- 4. Previous temporomandibular joint surgery
- 5. Systemic arthropathies
- 6. Fibromyalgia
- 7. Allergy to study medications
- 8. Traumatic injury of masticatory muscles or temporomandibular joint within last 12 months
- 9. Mandibular fracture within the last 12 months
- 10. Pregnancy or breastfeeding
- 11. Cervical radiculopathy or surgery
- 12. Prior Botox injection in the masticatory muscles
- 13. Initiation of additional treatment of MPD within the past 3 months

4.4 Lifestyle Considerations

Not Applicable

4.5 Screen Failures

Screen failures are defined as participants who consent to participate in the clinical trial but are not subsequently randomly assigned to the study intervention or entered in the study. A minimal set of screen failure information is required to ensure transparent reporting of screen failure participants, to meet the Consolidated Standards of Reporting Trials (CONSORT) publishing requirements and to respond to queries from regulatory authorities. Minimal information includes demography, screen failure details, eligibility criteria, and any serious adverse event (SAE).

4.6 Strategies for Recruitment and Retention

Physicians (neurologists, otolarygnologists, dentists) who would normally refer patients to oral and maxillofacial surgery at Weill-Cornell for treatment of myofascial pain disorder of the masticatory region will be made aware of the study and are welcome to refer patients for evaluation to participate in the study.

During the normal course of consultation in the office based environment, if a potential patient qualifies for participation in the research study, [name] will introduce the study and will obtain informed consent.

Study information will also be posted to social media sites, such as Facebook, Twitter and Instagram. IRB approved study fliers will be posted throughout the hospital to help boost enrollment

Participants in this study will be compensated for participation. The will receive \$25 on Clincards per study visit for 4 visits, for a total of \$100.

5. Registration Procedures

5.1 Subject Registration (WCM only)

Subjects will be registered within the WRG-CT as per the standard operating procedure for Subject Registration.

5.2 Subject Registration (Sub-sites)

Sub-sites will send subject enrollment log along with redacted consent forms to WCM study staff to confirm Subject Registration. Sub-sites will also be entering subject data into the REDCap database created for this study.

6. Study Procedures

6.1 Schedule of Assessments

Table 1. Schedule of trial events

	Pre-Study	Treatment Visit	1-Month Follow-Up	2-Month Follow-Up	3-Month Follow-Up
Informed Consent	Х				
Demographics	Х	X			
Medical history	Х	Х			
Interincisal		Х	Х	Х	Х
measurements		Х	Χ	^	X
Visual Analog Scale		X	X	X	X
Jaw Functional		Х	Х	Х	Х
Limitation Scale		^	^	^	^
SF-36		X	X	X	X
Botox/Placebo		Х			
Injection					
Adverse Event		Х	Х	Х	X
Assessment					

6.1.1 Pre-Study Visit

- Informed consent
- Inclusion/exclusion checklist
- Pharmacy order form completed and sent to pharmacy for randomization and processing
 - Eligible subjects will be randomly assigned to Botox injections or placebo treatment groups in a 1:1 ratio using a randomization scheme developed by the [name] and the Division of Biostatistics and Epidemiology, Department of Healthcare Policy & Research

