[name] is a full-time faculty member of the division of oral and maxillofacial surgery at Weill-Cornell Medicine. She practices the full scope of oral and maxillofacial surgery but has developed a special interest in minimally-invasive temporomandibular disorder treatment efforts including arthroscopic joint surgery and intra-muscular botulinum injections into the masticatory region for myofascial pain disorder. She currently has other research efforts in the area of temporomandibular joint disorder. She is collaborating with a scientist, [name], at Columbia University to grow stem cells from the cartilage, synovial tissues, and synovial fluids removed during the arthroscopic and open temporomandibular joint surgery Standard of care treatment for myofascial pain disorder at Weill Cornell/NYP involves the use of muscle relaxants, NSAIDS, warm compresses, night guards, and physical therapy. Botulinum injections into the masticatory muscles is a commonly performed adjudicative procedure for treatment of myofascial pain disorder at Weill-Cornell/NYP.

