3.1 Overall Design

for three months.

The proposed study is a randomized clinical trial comparing BTA to placebo injections into the masseter and temporalis muscles in management of myofascial pain disorder. The hypothesis is that injections of BTA reduces the intensity of myofascial pain more than placebo. Currently, in the literature, there is no evidence for the best non-surgical treatment modality for treatment of myofascial pain disorder of the muscles of mastication. Many different approaches have been described such as oral appliances, medications (NSAIDS and muscle relaxants), physiotherapy, acupuncture, trigger point injections, and botulinum injections. To date, the literature concerning trigger point injections and botulinum injections for treatment of myofascial pain disorders of the muscles of mastication is limited. Currently, injection of BTA is not FDA approved for myofascial pain disorder of the masseters and temporalis muscles.

Eligible participants in the clinical trial will be male and female adults ages 18 – 65 identified as having a myofascial pain diagnosis according to the research diagnostic criteria. All subjects will have myofascial pain disorder. Healthy controls will not be involved in the study. The study design will be a double-blind placebo controlled clinical trial. The participants will receive either a solution of placebo (total 4cc unpreserved 0.9% sodium chloride) injected into the masseters and temporalis muscles or a solution of botulinum toxin A (total of 100 units reconstituted with 4cc unpreserved 0.9% sodium chloride). Both treatment groups are considered investigative. The patients will be stratified into gender groups. The participants will be monitored

The primary outcome measure will be pain measured on a visual analog scale prior to treatment and at one, two and three months post-treatment. Secondary outcome measures performed at the same intervals will be quality of life (short form 36), maximum interincisal opening, and functional status via the jaw functional limitation scale. The only study procedures are the injection of botulinum toxin or placebo and the use of visual analog scale, measurement of maximum incisal opening and the use of visual analog scale and questionnaires.

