12.1 Study Design/Endpoints

Based on the preliminary data and the sample size calculations estimating a difference in mean prepost VAS change between groups of 1 point or greater (on a scale of 1-10), we plan to enroll a total of 110 subjects between the two study sites. Estimated 55 subjects will be enrolled at Weill-Cornell Medical Center/ New York Presbyterian Hospital and 55 subjects will be enrolled at the University of Illinois at Chicago. With 55 patients in the botulinum toxin A injection group and 55 patients in the placebo group (N=110), the study will have more than 90% power to detect a difference in mean in pre-post change between groups of 1.0 point or greater on VAS, using a two-sided t-test and assuming a standard deviation of 1.5 for the mean difference. This calculation allows for 10% attrition rate.

An intent-to-treat design will be followed and all subjects will have scheduled outcome evaluations until the end of the study, death of the subject, or subject refusal. Subjects will be withdrawn from their randomly assigned treatment for considerations of subject safety only. Descriptive statistics including mean, standard deviation, median, range, frequency, and percent will be calculated for the entire cohort as well as by the study arm (botulinum toxin A and unpreserved 0.9% sodium chloride) to assess the results of randomization and identify potential confounders.

The primary analyses of the data will be performed according to subjects' original treatment assignment (i.e., intention-to-treat analyses) and the inclusion of all data from all subjects randomized in the final analysis. To assess the primary endpoint of improvement of pain on a visual analog scale (VAS) between pre-op, 1, 2, and 3 months post-op, a repeated measure of analysis of variance will be performed with one between subject factor (botulinum toxin A versus placebo) and one within subject factor (time). This analysis will also be used for the secondary endpoints: function (MIO/jaw limitation scale) and quality of life (SF12). In the event of significant loss to follow-up, we will explore the use of a linear mixed model to assess the independent effect of the study group on VAS over the study visits. The paired t-test, or the signed-rank test as appropriate, will be used to assess change in pain, function, and QOL between pairs of relevant time points for both study arms.

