12.2 Sample Size/Accrual Rate

We plan to enroll 110 subjects in 18 months. About 55 subjects will be enrolled at Weill Cornell Medicine and the remaining 55 will be enrolled at the University of Illinois at Chicago.

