12.3 Stratification Factors

Not applicable

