12.4 Analysis of Endpoints

12.4.1 Analysis of Primary Endpoints

To assess the primary endpoint of improvement of pain on a visual analog scale (VAS) between pre-op, 1, 2, and 3 months post-op, a repeated measure of analysis of variance will be performed with one between subject factor (botulinum toxin A versus placebo) and one within subject factor (time). In the event of significant loss to follow-up, we will explore the use of a linear mixed model to assess the independent effect of the study group on VAS over the study visits.

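### Two clinics enrol about 55 patients each, but the planned model has no site term and the plan does not say whether allocation is blocked by site

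*Combined protocol and SAP*

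**What the plan says.** Enrolment is split evenly between two centres. Section 12.2: "About 55 subjects will be enrolled at Weill Cornell Medicine and the remaining 55 will be enrolled at the University of Illinois at Chicago". Section 7.7 places the injections in a separate clinic at each centre.

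On allocation, Section 6.1.1 says only that patients are "randomly assigned to Botox injections or placebo treatment groups in a 1:1 ratio using a randomization scheme". Section 7.11 adds who built the scheme and that the pharmacy holds it, but gives no blocks or strata. Section 3.1 and the synopsis name one factor: "The patients will be stratified into gender groups". Section 12.3, on stratification factors, is marked as not applicable. Site is not named as a factor anywhere.

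On analysis, Section 12.4.1 specifies a repeated-measures analysis of variance with "one between subject factor (botulinum toxin A versus placebo) and one within subject factor (time". Section 12.4.2 applies the same analysis to the secondary endpoints. If loss to follow-up is significant, "we will explore the use of a linear mixed model to assess the independent effect of the study group on VAS over the study visits"; no site term is named there either.

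**The concern.** Site can carry differences in usual care, injection technique and measurement. The plan leaves room for such differences. Section 2.3 describes care under "Standard of care treatment for myofascial pain disorder at Weill Cornell/NYP" and says nothing about the second centre. Section 7.8 records concomitant medication but sets no common regimen. Sections 7.6 and 7.7 fix a total volume but do not describe how it is divided among the muscles.

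If mean VAS change differs between the clinics, a model without site leaves that difference in the error, which widens the confidence interval and lowers power. The stated power of more than 90% has little slack once 10% attrition is taken off. If the list is not blocked by site, the arms can also differ by chance in their mix of sites, and in an unlucky draw that shifts the estimate.

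**Working it through.** **Inputs.** From Section 12.1: "With 55 patients in the botulinum toxin A injection group and 55 patients in the placebo group (N=110"), a difference of 1.0 VAS point in mean change, SD 1.5, two-sided t-test, 10% attrition, alpha 0.05. From Section 12.2: two sites of about 55. Assumed, because the documents give no value: a difference D between sites in mean VAS change of 0.25 to 1.5 points.

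**1. The plan's power.** The noncentrality is 1.0 / (1.5 × √(2/n)).
- n = 55 per arm: 3.496, power 93.4%.
- n = 49 per arm: 3.300, power 90.4%.
- The smallest n per arm that gives 90% is 49, and 49 / 0.9 = 54.4, rounded up to 55.

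The plan's figure reproduces, with less than half a point to spare at 49 per arm.

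**2. What site adds to the error.** Two equal sites whose mean change differs by D add D²/4 to the variance. Section 12.1 does not say whether 1.5 includes site, so both readings are shown. If 1.5 is the within-site SD, the SD without a site adjustment is √(1.5² + D²/4). If 1.5 is the total SD, the SD after adjustment is √(1.5² − D²/4). Power is at 49 per arm.

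| D | 1.5 within site: SD unadjusted | Power unadjusted | 1.5 total: SD adjusted | Power adjusted |
|---|---|---|---|---|
| 0 | 1.500 | 90.4% | – | – |
| 0.25 | 1.505 | 90.2% | 1.495 | 90.6% |
| 0.5 | 1.521 | 89.7% | 1.479 | 91.2% |
| 1.0 | 1.581 | 87.3% | 1.414 | 93.4% |
| 1.5 | 1.677 | 83.2% | 1.299 | 96.5% |

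On the second reading, the unadjusted power stays at the stated 90.4% whatever D is.

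**3. Chance imbalance if the list is not blocked by site.** With 55 per arm and 55 per site, the number k of one site's patients who fall in the botulinum arm is hypergeometric (110, 55, 55), with SD 2.63. The arms' site shares differ by (2k − 55)/55.
- A 30/25 split gives 5/55 = 9.1 points, so a difference of at least 10 points needs 31/24 or worse. The probability, in either direction, is 25%.
- A 33/22 split gives 11/55 = 20 points. That or worse has probability 5.6%.
- A 20-point difference shifts the estimate by 0.2 × D: 0.1 points at D = 0.5 and 0.2 at D = 1.0, against a target of 1.0.

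**4. Type I error.** Simulation with 20,000 trials per setting, 55 per arm, within-site SD 1.5, t-test without site:

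| D | List not blocked by site | List blocked by site |
|---|---|---|
| 0.5 | 5.0% | 4.7% |
| 1.0 | 4.9% | 4.0% |
| 1.5 | 5.3% | 3.1% |

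Without blocking by site the test keeps its level. With blocking but no site term it is conservative.

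**5. Which term does the work.** A constant site difference in VAS level cancels in pre-post change and in the arm-by-time test, but stays in the error for the arm main effect. A site difference in change enters the arm-by-time error and is removed only by a site-by-time term. Both terms are therefore needed.

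**The case against.** The strongest reply is that little is at stake and the documents do not show that the sites differ. Much of this stands.

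- **The scheme is not disclosed.** A reader might infer that allocation ignores site. The documents do not support that: the biostatistics division built the scheme, and its blocks and strata are not given. The entry in Section 12.3 is weak evidence, since it already conflicts with the gender stratification in Section 3.1. The supportable statement is that the method is not specified.
- **The second site's care is not described.** A reader might infer that background care differs. Silence is not a difference. Some features reduce variation: preparation by one pharmacy in a fixed total volume, common eligibility criteria including an exclusion for recently started treatment, and a primary outcome marked by the patient.
- **Chance imbalance is not bias.** A reader might call the 0.2-point shift a bias. It describes one unlucky draw. Over repeated randomization the estimate is unbiased, and type I error stays at about 5%.
- **The power loss is conditional.** It requires 1.5 to be a within-site SD, and a D of 1.0 equals the whole target effect. At D = 0.5 the loss is 0.7 points.
- **Some handling is planned.** Section 12.1 provides for by-arm descriptive statistics to look for confounders. That is not a prespecified adjustment for site.
- **Timing.** The protocol version is dated May 2022 and the synopsis gives December 31, 2022 under study duration, so a change to allocation may come too late. The model can still be changed.

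The model half of the point survives all of this. If the list is blocked by site, the analysis should reflect it; if it is not, the site terms absorb what blocking would have controlled.

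**Conclusion.** The point holds as a low-cost improvement to a stated model and as a gap in the description of allocation. It does not show that the trial is biased, that its false-positive rate is inflated or that its sample size is wrong. Someone reading only the larger power losses might conclude that the trial is underpowered. The documents do not support that, because they give no site difference and do not say which SD 1.5 is.

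The size depends on those two unknowns. At 49 per arm, the cost of omitting site against the stated power runs from nothing (1.5 is the total SD) through 0.7 points (within-site SD, D = 0.5) to 3.1 points at D = 1.0 and 7.2 at D = 1.5. The power figures treat the sites as equal in size and the arms as balanced within them. N need not change.

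**What to change.** **Sections 12.1, 12.4.1 and 12.4.2.** Add study site as a fixed between-subject factor, with site-by-time, to the repeated-measures analysis and to the fallback mixed model. Specify this before unblinding, so that the choice of covariates cannot depend on the results.

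**Section 12.3.** Replace the present entry with the stratification factors actually used, and say whether the list is blocked by site. Reconcile it with the gender stratification in the synopsis and Section 3.1; naming site alone would leave that conflict in place.

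**Allocation.** If randomization is still open and the list is not blocked by site, use permuted blocks within site for further patients while keeping gender. Otherwise keep the existing list and rely on the site terms.

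**Cost.** With 49 per arm, the between-subject error has 98 − 2 = 96 degrees of freedom and falls to 95. Site-by-time takes 3 of the 3 × 96 = 288 within-subject degrees of freedom. No new data are needed, since Sections 5.2 and 11.1 have each site enter its own patients in REDCap.

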6.1.2 Treatment Visit

- Pre-operative assessment
- Demographics
- Medical history
- Interincisal measurements
- Visual Analog Scale
- Jaw Functional Limitation Scale
- Short Form 36 Health Survey
- Botox/Placebo injections

6.1.3 Follow-up Phase

6.1.3.1 1-Month Visit

- Interincisal measurements
- Visual Analog Scale
- Jaw Functional Limitation Scale
- Short Form 36 Health Survey
- Adverse event assessments

6.1.3.2 2-Month Visit

- Interincisal measurements
- Visual Analog Scale
- Jaw Functional Limitation Scale
- Short Form 36 Health Survey
- Adverse event assessments

6.1.3.3 3-Month Visit

- Interincisal measurements
- Visual Analog Scale
- Jaw Functional Limitation Scale

- Short Form 36 Health Survey
- Adverse event assessments

7. Study Intervention

7.1 Study Intervention/Device Description

Botulinum Toxin A will be shipped directly to the Investigation Pharmacy from Allergan.

7.2 Availability

Botulinum Toxin A is an investigational agent supplied to investigators by Allergan.

7.3 Acquisition and Accountability

Half of the study materials will be shipped to the study site upon full execution of the agreement with Allergan and study approval by the IRB. Study material is shipped directly to the Investigational Pharmacy for storage and accountability.

The other half of the study materials will be shipped to the study site upon achieving 50% of the target enrollment and written confirmation that the study has been registered on www.clinicaltrials.gov.

7.4 Formulation, Appearance, Packaging, and Labeling

Not applicable

7.5 Product Storage and Stability

The product will be stored in the Investigational Pharmacy at WCM.

7.6 Preparation

Subjects will be receiving either a solution of placebo, a total of 4 cc unpreserved 0.9% sodium chloride, or a solution of botulinum toxin A, a total of 100 units reconstituted with 4 cc unpreserved 0.9% sodium chloride. Study drug will be prepared by the Investigational Pharmacy at WCM.

7.7 Dosing and Administration

Subjects will be receiving either a solution of placebo, a total of 4 cc unpreserved 0.9% sodium chloride, or a solution of botulinum toxin A, a total of 100 units reconstituted with 4 cc unpreserved 0.9% sodium chloride. Injections will take place in the Oral and Maxillofacial Surgery clinic on Baker 21 at WCM or at the University of Illinois at Chicago Oral Surgery clinic.

7.7.1 Dosing Delays/Dose Modifications

Not applicable

7.8 General Concomitant Medication and Supportive Care Guidelines

All concomitant medications will be recorded and/or updated on follow-up assessment form throughout the course of the study and saved in REDCap.

7.9 Duration of Therapy and Criteria for Removal from Study

Study Termination Guidelines: A subject's follow-up in the study will end after one of the follow applies:

- Subject's voluntary withdrawal
- Subject lost to follow-up
- Subject death
- Completion of all scheduled study follow-up appointments

